20.1.1.3. Dose Recommended by the BLRM Method

The dose allocation will start at the dose of 20 mg. Patients will be included by cohort of 1 to 6 patients. There must be at least 3 DLT evaluable patients at a specific dose level if there is a DLT observed in that level. After each cohort of patients is completed, the dose recommendation by the model will be based on posterior summaries including the mean, median, standard deviation, 95% credible interval, and the probability that the true DLT rate for each dose lies in one of the following categories:

- (0, 16%]: under-dosing
- (16%, 33%]: targeted toxicity
- (33%, 100%]: over-dosing

Following the principle of EWOC, after each cohort of patients the recommended dose by the model is the one with the highest posterior probability of the DLT rate falling in the targeted toxicity interval (16%, 33%] among the admissible doses fulfilling EWOC, i.e., it is unlikely (< 25% posterior probability) that the DLT rate at the dose falls in the over-dosing interval.

17.2.2 Final Recommendation and Stopping Rules

Dose escalation will continue until identification of the MTD(s) or suitable lower dose for recommended phase 2 dose(s) (the RP2D). This will occur when the following conditions are met:

1. At least 6 patients have been treated at this dose.
2. This dose satisfies one of the following conditions:
 - a. The posterior probability of targeted toxicity at this dose exceeds 50% and is the highest among potential doses, or
 - b. A minimum of 12 patients have already been treated on the trial.
3. It is the dose recommended for patients, by review of all clinical data by patients of the end of cohort meeting. Of note, the Dose Escalation part could be stopped earlier by a joint decision from the Sponsor and the Investigators during an SRC meeting, by considering the model estimations and a global assessment of the safety, PK, pharmacodynamics, and preliminary activity data.

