17.2.3.3 True Dose-DLT Scenarios

Simulations were performed on several true toxicity-dose relationships:

4. non-decreasing and finally reaching plateau
5. linear increasing (no plateau)
6. constant
7. increase steadily at the first beginning, and then increase much faster

Table13 True Underlying DLT Probabilities

Dose-limiting Toxicity (DLT) Scenarios	TP-0184 Dose Level (mg)							
	20	40	60	90	120	160	210	270
A	0.05	0.1	0.2	0.3	0.33	0.45	0.56	0.7
B	0.05	0.1	0.2	0.3	0.35	0.65	0.8	0.9
C	0.05	0.05	0.05	0.05	0.05	0.05	0.05	0.05
D	0.05	0.1	0.15	0.2	0.25	0.25	0.35	0.35

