17.2.3.4 Simulation Parameters

For each dose-DLT scenario, 5,000 clinical trial replications were generated using R software version 3.6.0 on a x86-64 architecture on a Windows OS. The Markov chain Monte Carlo (MCMC) estimation is obtained using R packages rjags and R2WinBUGS with 2,000 burn-in and 12,000 iterations on 2 chains (6,000 each). The seed used for MCMC estimation is 1 for chain 1 and 2 for chain 2.

Maximum number of patients of 30 was used. However, during the study, more patients may be added. The dose allocation rule used in the simulations is identical to the rule presented in [Section 20.1.1.3](#), ie, dose having the highest posterior probability of the DLT rate falling in the targeted interval (16%, 33%) among the admissible doses fulfilling EWOC.

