In general, when no DLTs are observed in 3 patients at a dose level, the decision is to increase the dose. When 1 DLT is observed in 3 patients, the decision is to stay at the current dose level or to escalate to the higher provisional dose level. When more than 1 DLT is observed in a 3-patient cohort, the decision is to decrease the dose level or to stay at the current level.

**APPENDIX 3. REVISED INTERNATIONAL PROGNOSTIC SCORING
SYSTEM (IPSS-R)**

IPSS-R Cytogenetic Risk Groups*, **

Cytogenetic prognostic subgroups	Cytogenetic abnormalities:
Very good	-Y, del(11q)
Good	Normal, del(5q), del(12p), del(20q), double including del(5q)
Intermediate	del(7q), +8, +19, +17q, any other single or double independent clones
Poor	-7, inv(3)/t(3q)/del(3q), double including -7/del(7q), Complex: 3 abnormalities
Very poor	Complex >3 abnormalities

IPSS-R Prognostic Score Values*

Prognostic variable	0	0.5	1	1.5	2	3	4
Cytogenetics	Very Good	-	Good	-	Intermediate	Poor	Very Poor
BM Blasts (%)	≤2	-	>2 - <5	-	5 - 10	>10	-
Hemoglobin (g/dL)	≥10	-	8 - <10	<8	-	-	-
Platelets (x10 ⁹ /L)	≥100	50 - <100	<50	-	-	-	-
ANC (x10 ⁹ /L)	≥0.8	<0.8	-	-	-	-	-

IPSS-R Prognostic Risk Categories/Scores*

Risk Category	Risk Score
Very Low	≤1.5
Low	>1.5 - 3
Intermediate	>3 - 4.5
High	>4.5 - 6
Very High	>6

IPSS-R: Prognostic Risk Category Clinical Outcomes*

	No. pts	Very Low	Low	Intermediate	High	Very High
Subjects (%)	7012	19%	38%	20%	13%	10%
Survival***	-	8.8	5.3	3.0	1.6	0.8
AML/25%**^	-	NR	10.8	3.2	1.4	0.7

**Median, year.

^Median time to 25% AML evolution.

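### Table 14, the only operating characteristics stated for dose escalation, is wrong as written and cannot come from the allocation and stopping rules of Appendix 2

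*Protocol*

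**What the plan says.** All references are to Protocol Appendix 2 unless stated otherwise.

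- **Allocation (20.1.1.3).** The model recommends the dose with the highest posterior probability of a DLT rate in (16%, 33%], among doses whose posterior probability of a rate above 33% is below 25% (EWOC). Cohorts may hold 1 to 6 patients.
- **Stopping (17.2.2).** Three conditions apply. Condition 1: "At least 6 patients have been treated at this dose". Condition 2 is met by either 2a, "The posterior probability of targeted toxicity at this dose exceeds 50% and is the highest among potential doses, or" 2b, "A minimum of 12 patients have already been treated on the trial". Condition 3: "It is the dose recommended for patients, by review of all clinical data".
- **Simulation (17.2.3.4).** "The dose allocation rule used in the simulations is identical to the rule presented in" 20.1.1.3. On trial size: "Maximum number of patients of 30 was used". There were 5,000 replicates per scenario. Neither the stopping rule nor the cohort size simulated is stated.
- **Truths (Table 13).** In scenario C every dose has a 5% DLT rate. In scenario D only 210 and 270 mg exceed 33% (both 35%).
- **Results (Table 14).** Mean patients per trial in A to D are 21.3, 20.8, 26.2 and 21.1. No MTD is recommended in 0.19, 0.207, 0.985 and 0.19 of trials.

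**The concern.** Phase 2 runs at the dose carried out of Phase 1, and Protocol 13.1.8.2 says that dose usually has a DLT rate between 16% and 33%. Table 14 is what a reader would use to judge whether the design finds such a dose, how many patients it needs, and whether a count of 12 is a reasonable alternative to the posterior test. If its entries contradict each other or the stated rules, none of these can be judged from it.

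**Working it through.** **1. DLTs in scenario C.** Inputs: rate 0.05 at every dose (Table 13); mean 26.2 patients and 0.1 DLTs per trial (Table 14). When all doses share one rate, expected DLTs = rate × mean number treated, under any allocation or stopping rule (Wald's identity):

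0.05 × 26.2 = 1.31, against 0.1 stated.

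Simulation noise does not explain the gap. The standard deviation per trial is about √(30 × 0.05 × 0.95) = 1.19, so the standard error over 5,000 trials is about 1.19/√5000 = 0.017.

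**2. Exposure columns.** Section 20.1.1.3.1 defines these as the average number of patients per trial exposed at under-, target- and over-toxicity doses. The three categories cover every dose, so each row should sum to the mean trial size.

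| Scenario | Sum of the columns | Stated mean N |
|---|---|---|
| A | 0.3 + 10.3 + 0 = 10.6 | 21.3 |
| B | 0.9 + 5.2 + 1.8 = 7.9 | 20.8 |
| C | 0.3 + 0 + 0 = 0.3 | 26.2 |
| D | 1.8 + 3 + 5.4 = 10.2 | 21.1 |

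Scrambled table columns are not the cause: the selection entries for C sit where they should and sum to one (0.015 + 0 + 0 + 0.985).

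**3. Rebuilding the model.** The posterior was computed by numerical integration with the Table 11 prior and the 90 mg reference dose. It reproduces Table 12: at 90 mg, under/target/over 0.262/0.281/0.457 against 0.2602/0.282/0.4578. Table 15 rows 1, 3 and 5 to 9 match within 0.02. Row 2 (P(over) 0.262 against 0.2312) and row 4 (P(target) 0.469 against 0.5059) are off by 0.03 to 0.04.

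**4. Scenario D.** Table 14 gives 0.303 for recommending a dose with a true rate above 33%, which means 210 or 270 mg. Table 12 puts prior P(over) at 0.9999 and 1 for these doses, against a limit of 0.25. The allocation rule was followed with no stopping, through every DLT pattern up to 30 patients, for cohorts of 3, 4, 5 and 6, with and without skipping:

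- It never recommends a dose above 120 mg.
- The smallest P(over) is 0.75 at 160 mg, and above 0.99 at 210 mg.
- Simulated cohorts of 1, 2 and random 1 to 6 (scenarios C and D) reach 0.73 at 160 mg and also never go above 120 mg.
- Even 30 DLT-free patients, all at 120 mg, leave 160 mg at 0.59 and 210 mg at 0.99.

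An error of 0.03 to 0.04 in the rebuild cannot close that gap.

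**5. Scenario C, no MTD.** Table 14 gives 0.985, with quartiles of 30-30-30 patients. The rule of 17.2.2 was simulated with 2b active, the model recommendation followed, the fixed dose grid and a cap of 30 (5,000 trials per setting). With cohorts of 3 or 4 a dose is declared in 97-98% of trials and the largest trial has 28 patients. Over cohorts of 1, 2, 5, 6 or random 1 to 6, a dose is declared in 70-99%. With 2b removed, so that only 2a can stop escalation, no MTD is reached in 12% to 85%. No variant tried gives 98.5%.

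**6. How 2b behaves.** Take a DLT-free run of 3 patients at 20 mg, 3 at 60 mg and 6 at 90 mg. At N = 12, 90 mg has under/target/over 0.75/0.23/0.02. Condition 2a fails; conditions 1 and 2b hold. In A, B and D with cohorts of 3 or 4, 2b alone ends 63-84% of trials and mean N is 13.2 to 18.3. Moving the EWOC limit to 0.22 or 0.28, the 2a threshold to 0.47, or 0.28 and 0.47 together, widens the 2b share to 48-87%.

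**The case against.** **The exposure columns may only be mislabelled.** Dividing each non-zero exposure by its selection probability gives 7.9 and 13.4 (A), 8.6, 10.7 and 9.0 (B), 20 (C), and 9.9, 9.2 and 17.8 (D). All are at least 6, as condition 1 would produce if the columns counted only patients at the declared dose. That is plausible, but 20.1.1.3.1 defines the metric otherwise. It also does not rescue the DLT column: in A, 5 DLTs on 10.6 patients would be 47%, while that row shows no exposure above 33%.

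**Section 17.2.3.4 claims identity for the allocation rule only.** This stands. Scenario C's no-MTD rate conflicts with the stopping rule, not with that sentence. Scenario D conflicts with the allocation rule itself.

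**Not every entry misleads.** This also stands. Target selection in A (0.771) and D (0.326) lies inside the range found for the written rule, and cohorts of 5 give mean N of 20 to 22, close to Table 14.

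**The committee could open higher doses.** In the trial, yes: the model is guidance, intermediate doses are allowed, and 17.2.4 says that "when no DLTs are observed in 3 patients at a dose level, the decision is to increase the dose". The simulations, however, are described as following the model rule.

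**A stronger reading is tempting:** that 2b is itself an error, or unsafe, and must be joined to 2a. The documents do not support it. A dose that meets 2b still needs 6 patients, the committee's recommendation and, where the model is followed, EWOC. Section 17.2.2 expressly allows a lower dose judged suitable to go forward. Most of the Table 14 faults have nothing to do with 2b. The share of stops due to 2b alone is also not firm, because the rebuild misses Table 15 row 4 right at the 2a threshold; a separate set of runs gave 41-95%.

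**Conclusion.** The point holds for Table 14. The DLT count in scenario C (0.1 against 1.31) and the exposure sums are wrong on the documents alone. The 0.303 in scenario D cannot arise from the stated prior and allocation rule. The 0.985 in scenario C is not reproduced by the stopping rule under any cohort size tried. The last two rest on the rebuilt model, which matches Table 12 and most of Table 15; the last also assumes that the model recommendation is followed on the fixed grid, with cohort size varied because none is stated.

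Whether 12 patients is enough remains an open design question, which a correct table would let the sponsor answer. This is a should-fix matter about the design as written: SAP section 2 records termination after two patients, so the rule had no practical effect here.

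**What to change.** Re-run and replace Table 14 under the exact rules of 20.1.1.3 and 17.2.2 with the Table 11 prior. State the cohort size, whether dose levels may be skipped, and what happens at 30 patients. Before release, check that the exposure columns sum to mean N in every row and that scenario C DLTs equal 5% of mean N. Add the proportion of trials in which 2b ends escalation without 2a being met. This costs computing time and no patients.

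Optional: require 2a and 2b together, and at the cap carry forward the model-recommended EWOC-admissible dose with a note that 2a was not met. This is a trade-off. It adds about 6-8 Phase 1 patients on average in A, B and D (5-11 in C), inside the planned 30. With cohorts of 3 or 4 and that fallback, selection of a target-interval dose in A rises from 66-78% to 81-84%. Without the fallback the gain is not assured: in two settings A moved from 73 to 76% and from 79 down to 72%.

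Minor wording: condition 1 counts treated patients, while Protocol 13.1.5 bases escalation on DLT-evaluable patients. Counting evaluable patients would align the two.

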17.2.3 Operating Characteristics

17.2.3.2 Introduction

This section presents the operating characteristics illustrating the precision of the design in estimating the MTD under various assumed true dose-toxicity relationship.

17.2.3.3 True Dose-DLT Scenarios

Simulations were performed on several true toxicity-dose relationships:

4. non-decreasing and finally reaching plateau
5. linear increasing (no plateau)
6. constant
7. increase steadily at the first beginning, and then increase much faster

Table13 True Underlying DLT Probabilities

Dose-limiting Toxicity (DLT) Scenarios	TP-0184 Dose Level (mg)							
	20	40	60	90	120	160	210	270
A	0.05	0.1	0.2	0.3	0.33	0.45	0.56	0.7
B	0.05	0.1	0.2	0.3	0.35	0.65	0.8	0.9
C	0.05	0.05	0.05	0.05	0.05	0.05	0.05	0.05
D	0.05	0.1	0.15	0.2	0.25	0.25	0.35	0.35

17.2.3.4 Simulation Parameters

For each dose-DLT scenario, 5,000 clinical trial replications were generated using R software version 3.6.0 on a x86-64 architecture on a Windows OS. The Markov chain Monte Carlo (MCMC) estimation is obtained using R packages rjags and R2WinBUGS with 2,000 burn-in and 12,000 iterations on 2 chains (6,000 each). The seed used for MCMC estimation is 1 for chain 1 and 2 for chain 2.

Maximum number of patients of 30 was used. However, during the study, more patients may be added. The dose allocation rule used in the simulations is identical to the rule presented in [Section 20.1.1.3](#), ie, dose having the highest posterior probability of the DLT rate falling in the targeted interval (16%, 33%) among the admissible doses fulfilling EWOC.

20.1.1.3.1. Evaluation Metrics

Operating characteristics were reviewed for the simulations to compare the relative performance of the design under each true dose-DLT relationship. The following metrics were:

- Probability of recommending as the MTD:
 - An under-toxicity dose level, i.e., a dose with true probability of DLT in the under-toxic interval (0%, 16%) (Sponsor risk)
 - A targeted-toxicity dose level, i.e., a dose with true probability of DLT in the targeted-toxicity interval (16%, 33%) (correct final decision)
 - An over-toxicity dose level, i.e., a dose with true probability of DLT in the over toxicity interval (33%, 100%) (patient risk)
- Average number of patients per trial exposed at:
 - An under-toxicity dose level, as defined above
 - A targeted-toxicity dose level, as defined above
 - An over-toxicity dose level, as defined above
- Summary of the total number of patients per trial (mean, first quartile, median, third quartile)
- Average total number of DLTs observed per trial

20.1.1.3.2. Operating Characteristics of the Design

Operating characteristics of the final design are reviewed to investigate performance of the model under each true dose-DLT scenario.

[Table 14](#) summarizes the results from the simulations performed.

Table 14: Summary Metrics of the Simulations Performed

DLT scenario	Probability of Recommending a Dose with true Pr(DLT)			No MTD Recommended	Average Number of Patients Per Trial Receiving a Dose with True Pr(DLT)			Average Number of Patients	
	[0, 0.16]	(0.16, 0.33]	(0.33, 1]		(0, 0.16]	(0.16, 0.33]	(0.33, 1]	Per Trial (Q1-Median-Q3)	Experiencing a DLT per Trial
A	0.038	0.771	0	0.19	0.3	10.3	0	21.3 (22-22-26)	5
B	0.105	0.487	0.201	0.207	0.9	5.2	1.8	20.8 (22-22-26)	5
C	0.015	0	0	0.985	0.3	0	0	26.2 (30-30-30)	0.1
D	0.181	0.326	0.303	0.19	1.8	3	5.4	21.1 (22-22-26)	4.7

Abbreviations: MTD = maximum tolerated dose; P(DLT) = DLT rate; Q1 = the first quartile; Q3 = the third quartile.

17.2.4 Hypothetical Dose Allocation Scenarios in Early Cohorts

Aside from the overall operating characteristics studied above, the design should make reasonable decisions during a study based on the observed DLTs. After completion of a given dose level, the dose allocation for the subsequent dose level will depend on the recommendation of the model and medical review of all available data.

Some scenarios to illustrate on-study dose allocation are presented in [Table 15](#). These scenarios assume that each dose level has 3 or more evaluable patients and the next recommended dose is based on the rule defined in [Section 20.1.1.3](#), with the provisional doses specified in [Table 15](#). However, during the study it may be possible to add new provisional dose levels.

Table 15: Hypothetical Dose Allocation Scenarios in Early Cohorts

Scenario	Dose (mg)	Npat	Ntox	NDL	P(target) at NDL	P(overtox) at NDL	DLT Rate median at NDL
1	20	3	0	60	0.2314	0.1462	0.102
2	20, 40	3, 3	0, 0	90	0.3905	0.2312	0.205
3	20, 40, 60	3, 3, 3	0, 0, 0	90	0.3571	0.1501	0.162
4	20, 40, 60, 90	3, 3, 3, 4	0, 0, 0, 1	90	0.5059	0.1293	0.193
5	20, 40, 60, 90, 120	3, 3, 3, 3, 4	0, 0, 0, 0, 1	90	0.2547	0.0269	0.109
6	20, 40, 60, 90, 120	3, 3, 3, 4, 4	0, 0, 0, 0, 1	90	0.2426	0.0194	0.106
7	20, 40, 60, 90, 120, 160	3, 3, 3, 3, 3, 4	0, 0, 0, 0, 0, 1	120	0.6128	0.1222	0.207
8	20, 40, 60, 90, 120, 160	3, 3, 3, 3, 4, 6	0, 0, 0, 0, 0, 1	120	0.5706	0.0503	0.178
9	20, 40, 60, 90, 120, 160	3, 3, 3, 3, 4, 6	0, 0, 0, 0, 0, 1	120	0.5706	0.0503	0.178

[figure not shown]
Abbreviations: DLT = Dose-limiting toxicity; EWOC = Escalation with overdose control; NDL = Next dose level; Npat = Number of patients; Ntox = Number of toxicities.

[figure not shown]
P(target) at NDL: posterior probability that the true DLT rate for the next recommended dose lies in the targeted interval (16%, 33%).

[figure not shown]
P(overtox) at NDL: posterior probability that the true DLT rate for the next recommended dose lies in the excessive toxicity interval (33%, 100%).

17.2.5 Hypothetical Dose Allocation Scenarios in Early Cohorts: Visualize Interval Probabilities by Dose

Scenario 1: 0/3 pts at 20 mg

Scenario 2: 1/4 pts at 90 mg

Scenario 3: 2/4 pts at 90 mg

In general, when no DLTs are observed in 3 patients at a dose level, the decision is to increase the dose. When 1 DLT is observed in 3 patients, the decision is to stay at the current dose level or to escalate to the higher provisional dose level. When more than 1 DLT is observed in a 3-patient cohort, the decision is to decrease the dose level or to stay at the current level.

**APPENDIX 3. REVISED INTERNATIONAL PROGNOSTIC SCORING
SYSTEM (IPSS-R)**

IPSS-R Cytogenetic Risk Groups*, **

Cytogenetic prognostic subgroups	Cytogenetic abnormalities:
Very good	-Y, del(11q)
Good	Normal, del(5q), del(12p), del(20q), double including del(5q)
Intermediate	del(7q), +8, +19, +17q, any other single or double independent clones
Poor	-7, inv(3)/t(3q)/del(3q), double including -7/del(7q), Complex: 3 abnormalities
Very poor	Complex >3 abnormalities

IPSS-R Prognostic Score Values*

Prognostic variable	0	0.5	1	1.5	2	3	4
Cytogenetics	Very Good	-	Good	-	Intermediate	Poor	Very Poor
BM Blasts (%)	≤2	-	>2 - <5	-	5 - 10	>10	-
Hemoglobin (g/dL)	≥10	-	8 - <10	<8	-	-	-
Platelets (x10 ⁹ /L)	≥100	50 - <100	<50	-	-	-	-
ANC (x10 ⁹ /L)	≥0.8	<0.8	-	-	-	-	-

IPSS-R Prognostic Risk Categories/Scores*

Risk Category	Risk Score
Very Low	≤1.5
Low	>1.5 - 3
Intermediate	>3 - 4.5
High	>4.5 - 6
Very High	>6

IPSS-R: Prognostic Risk Category Clinical Outcomes*

	No. pts	Very Low	Low	Intermediate	High	Very High
Subjects (%)	7012	19%	38%	20%	13%	10%
Survival***	-	8.8	5.3	3.0	1.6	0.8
AML/25%**^	-	NR	10.8	3.2	1.4	0.7

**Median, year.

^Median time to 25% AML evolution.

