20.1.1.2. Prior Specifications

The bivariate normal prior for the BLRM parameters with a reference dose level of 90 mg is obtained as follows:

The following noninformative prior for $(\log(\alpha), \log(\beta))$ was used:

- The mean of $\log(\alpha)$ was set to -0.847 and mean of $\log(\beta)$ was set to 0.913 to allow the median DLT rate to be around 1%.
- The standard deviation of $\log(\alpha)$ was set to 1.275, and the standard deviation of $\log(\beta)$ to 0.482, which allows for considerable prior uncertainty for the dose-toxicity profile.
- The correlation between $\log(\alpha)$ and $\log(\beta)$ was set to -0.9.

Table 11 Prior Parameters for Bivariate Normal Distribution of Model Parameters

Parameters	Means	Standard Deviations	Correlation
$\log(\alpha), \log(\beta)$	(-0.847, 0.913)	(1.275, 0.482)	-0.9

Table 12 Prior Distribution Summaries Derived from Priors in Table 11

TP-0184 Dose (mg)	Prior Probabilities Pr(DLT) is in Interval:			Mean	SD	Quantiles		
	(0, 0.16]	(0.16, 0.33]	(0.33, 1]			2.5%	50%	97.5%
20	0.8685	0.0744	0.0571	0.06784	0.13677	0	0.0101	0.5253
40	0.7191	0.1414	0.1395	0.13674	0.18611	0.00026	0.05436	0.6946
60	0.5463	0.2089	0.2448	0.21414	0.21583	0.00324	0.1354	0.77793
90	0.2602	0.282	0.4578	0.34556	0.22766	0.03638	0.3026	0.84387
120	0.0303	0.2178	0.7519	0.48932	0.20034	0.15282	0.47701	0.87993
160	0	0.0119	0.9881	0.66399	0.14196	0.37032	0.67276	0.91269
210	0	1e-04	0.9999	0.80101	0.09715	0.57776	0.81558	0.95098
270	0	0	1	0.88234	0.06829	0.72003	0.89404	0.98476

Note: Bold doses indicate not meeting the overdose control criterion (more than 25% chance of over-dosing) with the prior information only.

Abbreviation: DLT = dose-limiting toxicity.

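### Two rows of Table 15 do not match the stated model, prior and data, and in scenario 2 the exact overdose probability at the printed next dose is above the protocol's 25% limit

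*Protocol*

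**What the plan says.** Appendix 2 of the protocol models the DLT probability by a two-parameter logistic curve in log dose with reference dose 90 mg. Table 11 gives the bivariate normal prior for (log α, log β): means -0.847 and 0.913, standard deviations 1.275 and 0.482, correlation -0.9.

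Section 20.1.1.3 recommends the dose with the highest posterior probability that the DLT rate lies in (16%, 33%], among doses for which "it is unlikely (< 25% posterior probability) that the DLT rate at the dose falls in the over-dosing interval". Section 7.3.1 (Phase 1 Dose Escalation) and SAP Section 1.1 state the same limit as at most 25%.

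Section 17.2.4 says of the scenarios in Table 15 that "the next recommended dose is based on the rule defined in" Section 20.1.1.3. Two rows matter here:

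- Scenario 2: 0/3 at 20 mg and 0/3 at 40 mg; next dose 90 mg, P(target) 0.3905, P(overtox) 0.2312.
- Scenario 4: 0/3 at 20, 40 and 60 mg and 1/4 at 90 mg; next dose 90 mg, P(target) 0.5059, P(overtox) 0.1293.

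A 50% threshold on P(target) appears in two rules. Condition 2a of the rule for ending escalation (Appendix 2, 17.2.2) reads "The posterior probability of targeted toxicity at this dose exceeds 50% and is the highest among potential doses". Sections 7.3.4 and 13.1.8.3 use a similar criterion to suspend enrollment.

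For the simulations, Section 17.2.3.4 describes MCMC in R "with 2,000 burn-in and 12,000 iterations on 2 chains (6,000 each"). No settings are given for Table 15 itself. SAP Section 3 says that R was used for BLRM monitoring.

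**The concern.** The model has two parameters and the appendix gives every input, so each probability in Table 15 can be checked exactly. In two rows the printed figure and the exact figure fall on opposite sides of a threshold that the protocol uses.

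Scenario 2 matters more. It is the ordinary path after two clean cohorts, and Section 7.3.1 presents overdose control as the guard against exposing patients to toxic doses. A worked example whose recommendation fails that guard misleads anyone who uses the table to judge how the rule behaves. It also leaves open whether the code behind it computes the posterior accurately enough near the 25% cut.

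**Working it through.** **Inputs.** Prior from Table 11; reference dose 90 mg and model from Appendix 2 (Statistical Model); intervals from Section 20.1.1.3; data from each row of Table 15.

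**Model.** logit π(d) = log α + β log(d/90). The posterior is proportional to the prior times the product over doses of π(d)^t × (1 − π(d))^(n − t), with t DLTs in n patients. For scenario 2 the likelihood is (1 − π(20))³ × (1 − π(40))³.

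**Step 1: reproduce the plan's prior (Table 12).** At 90 mg the log-dose term is zero, so logit π(90) = log α, and Table 12 can be checked by hand:

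- logit 0.33 = −0.708. P(log α > −0.708) = 1 − Φ((−0.708 + 0.847)/1.275) = 1 − Φ(0.109) = 0.457. Table 12: 0.4578.
- logit 0.16 = −1.658. P(log α ≤ −1.658) = Φ((−1.658 + 0.847)/1.275) = Φ(−0.636) = 0.262. Table 12: 0.2602.

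Numerical integration over both parameters matches every interval probability in Table 12 to within 0.005. The prior and model have therefore been read as the protocol meant them.

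**Step 2: recompute Table 15.** The values below use quasi-random integration over the prior (2²² points). Two-dimensional grid integration agrees to within about 0.002. Both probabilities are at the printed next dose.

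| Scenario | Next dose (mg) | P(target) printed | P(target) exact | P(overtox) printed | P(overtox) exact |
|---|---|---|---|---|---|
| 1 | 60 | 0.2314 | 0.220 | 0.1462 | 0.145 |
| **2** | 90 | **0.3905** | **0.361** | **0.2312** | **0.262** |
| 3 | 90 | 0.3571 | 0.369 | 0.1501 | 0.148 |
| **4** | 90 | **0.5059** | **0.469** | 0.1293 | 0.149 |
| 5 | 90 | 0.2547 | 0.274 | 0.0269 | 0.028 |
| 6 | 90 | 0.2426 | 0.246 | 0.0194 | 0.020 |
| 7 | 120 | 0.6128 | 0.617 | 0.1222 | 0.120 |
| 8 and 9 (identical) | 120 | 0.5706 | 0.555 | 0.0503 | 0.051 |

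Outside rows 2 and 4 the largest difference is 0.019 (scenario 5, P(target)), and applying the rule to the exact values gives the printed next dose.

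**Step 3: compare with the thresholds.**

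- Scenario 2: P(overtox) is understated by 0.262 − 0.231 = 0.031. The exact value exceeds the limit by 0.262 − 0.250 = 0.012, so it fails under either wording (below 25%, or at most 25%).
- Scenario 4: P(target) is overstated by 0.506 − 0.469 = 0.037 (0.468 to 0.470 across methods) and lies about 0.03 below 50%. P(overtox) of 0.149 keeps 90 mg admissible, and the next dose is unchanged.

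**Step 4: try to rescue the printed figures.**

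- *Prior correlation.* Values of −0.85, −0.95, 0 and +0.9 move neither figure across its threshold. The closest is −0.95, with 0.255 in scenario 2 and 0.475 in scenario 4.
- *Patient counts, scenario 2.* With 4 and 4 patients at 20 and 40 mg, P(overtox) is about 0.23, near the printed value, but P(target) is about 0.37 against 0.3905. This is a partial match, and those are not the listed data.
- *Listed data, scenario 4.* The closest variant tried moved the DLT to 60 mg and put 6 patients at 90 mg (P(target) 0.514, P(overtox) 0.123). That is also not the row as printed.
- *Monte Carlo error.* In 200 repeated runs of two chains of 6,000 draws, scenario 2 P(overtox) had a standard deviation of 0.021 with a slowly mixing sampler and 0.0095 with a better-mixing one. It fell below 0.25 in 28% and 11% of runs. The printed 0.2312 is about 1.5 and 3.3 standard deviations from the run means; the printed 0.5059 in scenario 4 is about 2.8 and 4.8.

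**The case against.** The strongest reply is that this is a small discrepancy in an illustrative table. The protocol treats the BLRM output as guidance, to be combined with safety, PK and clinical review, and the Safety Review Committee (SRC) meets before each escalation. On-study decisions would use a posterior from actual data. The exact scenario 2 value is only 0.012 above the limit. SAP Section 2 says that the study was terminated after two patients and plans listings only. All of this stands and lowers the severity. It does not make the printed recommendation consistent with the rule that the table claims to apply.

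A reader might infer more than the documents support:

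- *That Table 15 as a whole fails.* It does not; only rows 2 and 4 do.
- *That the MCMC engine is at fault, and Table 14 and on-study monitoring with it.* The stated settings belong to the simulations, and Table 14 was not recomputed here. A listing error is also possible: rows 8 and 9 are identical, and the scenario labels in 17.2.5 (scenario 2 as 1/4 at 90 mg, scenario 3 as 2/4 at 90 mg) do not match the table. Standard errors based on 12,000 independent draws would overstate the evidence, because chain draws are correlated.
- *That scenario 4 wrongly ends escalation.* Ending needs at least 6 patients at the dose and the row has 4. Condition 2b (12 patients on trial) is already met with 3 + 3 + 3 + 4 = 13, so 2a is not needed. The 50% figure bears mainly on the enrollment-suspension trigger, which states no minimum number but also requires the highest P(target) among the dose levels and leads to SRC review.

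**Conclusion.** The point holds for two rows. In scenario 2 the exact overdose probability at 90 mg is 0.262 against 0.2312 printed, so the printed recommendation does not meet the 25% limit in Sections 7.3.1 and 20.1.1.3 and SAP Section 1.1. In scenario 4 the exact target probability is about 0.47 against 0.5059 printed, with no change of dose and no effect on the rule for ending escalation.

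This rests on the model, prior and data as printed; the agreement with Table 12 and with the other rows of Table 15 makes a misreading unlikely. The accurate statement is that the printed figures do not match the listed inputs. Whether the computation or the listing is at fault cannot be settled from the documents. Severity is moderate: the correction matters for the protocol record and for reuse of the design or code, and nothing in the documents shows that a patient's dose was affected.

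**What to change.** - Recompute Table 15 with a deterministic two-parameter posterior, or with an MCMC run whose convergence and Monte Carlo error are documented and small relative to the distance from the 25% and 50% cuts.
- Correct rows 2 and 4, or their listed inputs if those are what is wrong. Resolve the duplicate rows 8 and 9 and the mismatched scenario labels in 17.2.5.
- Reconcile the scenario 2 recommendation with the overdose rule. Which dose should follow is for the sponsor and the SRC; none is proposed here.
- Confirm that the code used for on-study BLRM monitoring and for Table 14 reproduces the exact posterior, for example on the Table 15 rows.

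The cost is a few hours of programming and a corrected appendix table. No extra patients are needed, and no rule, prior or endpoint changes.
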